10.3 Analysis of Exploratory Endpoints

The analyses of PK and PD exploratory endpoints are described in [Sections 12 and 13](#) respectively.

For efficacy the following exploratory endpoint analyses will be performed, including changes from baseline as applicable. For all measures, the ATS Analysis Set will be used. No imputation will be performed for missing values.

10.3.1 Time to Event Analysis

The following events will be analyzed only for treatment-naïve subjects:

- Time from Visit Day 1 to start of first HAE attack.
- Time to first HAE attack after Day 14.
- Time from end of first HAE attack to start of second HAE attack. (only for subjects experiencing at least one attack).
- Time from end of second to start of third HAE attack (only for subjects experiencing a second attack).

The following will be analyzed for all subjects in the ATS Analysis Set instead of only for treatment-naïve subjects:

- Maximum attack-free time.

The time to event will be derived as described in [Section 8.2.2](#) within the Treatment/Efficacy evaluation period.

Attack-free time between subsequent HAE attacks is calculated as start date/time of the following HAE attack – end date/time of the preceding HAE attack. Subjects with no HAE attack or no second or third HAE attack will be censored at EOT Visit.

For each of the HAE events (1st, 2nd, 3rd attack and 1st attack after Day 14) the following will be displayed:

- The number and percentage of subjects who do not experience the event.
- The median time, the 25% and 75% percentile times of subjects being event-free / having no second / having no third HAE attack, respectively. The median, 25%, and 75% percentile times are defined as the times for which the Kaplan-Meier estimates for the time-to-event functions are equal 0.5, 0.25, and 0.75, respectively.

If the time to event function is horizontal at 25%, 50% or 75%, the median or percentiles will be calculated as the average of the two values between which the time-to-event function is horizontal.

- The minimum and maximum times to the event.

Kaplan-Meier curves with 95% CI will be plotted showing the percentage of subjects being event-free at certain times.

The corresponding life tables will also be presented.

The maximum attack-free time will be summarized by the median time, the 25% and 75% percentile times and the minimum and maximum times to the event.

The number and percentage of subjects who have a maximum attack-free time of at least 6 months and of at least 12 months will also be displayed in the summary for maximum attack-free time.

By-subject listings will be provided with time until the first, the second and the third HAE attack as applicable, or until EOT Visit with indication whether the observation is censored. The maximum attack-free time will be flagged.

10.3.2 Quality of Life Endpoints

Investigator's Global Assessment of Response to Therapy

The IGART will require the investigator to rate subjects using the following direction (or an appropriate translation, as applicable): “Considering all of the ways HAE affects your patient, please rate your patient’s response to the study medication provided to prevent HAE attacks during this Treatment Period”. Whenever possible, the same investigator will perform the IGART for each subject throughout the study.

The following ratings can be chosen by the investigator:

- none – worse or no response at all, not acceptable;
- poor – very little response, not acceptable;
- fair – some response, acceptable but could be better;
- good – good response, acceptable;
- excellent – excellent response, as good as can be imagined.

TSQM II

The TSQM II consists of 11 items of which 8 items are made up of 3 specific scales (EFFECT, SIDE EFFECTS and CONVENIENCE) and 2 global satisfaction scale (GLOBAL); one item (Item 3) questions if as a result of taking this medication, the subject experiences any side effects at all, which can be answered by yes and no. Scale scores are calculated for each scale and are transformed into scores ranging from 0 to 100.

The scale scores are calculated as:

EFFECT

$$[(\text{Item 1} + \text{Item 2}) - 3] \text{ divided by } 12 \times 100.$$

If one item is missing:
$$[(\text{Sum of Available Items}) - 2] \text{ divided by } 6 \times 100.$$

SIDE EFFECTS

$$[(\text{Sum of Item 4 to Item 6}) - 3] \text{ divided by } 12 \times 100.$$

If one item is missing:
$$[(\text{Sum of Available Items}) - 2] \text{ divided by } 8 \times 100.$$

CONVENIENCE

$[(\text{Sum of Item 7 to Item 9}) - 3] \text{ divided by } 18 \times 100.$

If one item is missing: $[(\text{Sum of Available Items}) - 2] \text{ divided by } 12 \times 100.$

GLOBAL

$[(\text{Sum of Item 10 to Item 11}) - 2] \text{ divided by } 12 \times 100.$

If one item is missing: $[(\text{Sum of Available Items}) - 1] \text{ divided by } 6 \times 100.$

If more than one item is missing from any subscale then the subscale will not be calculated.

WPAI:GH

The WPAI:GH yields four types of scores: 1. Absenteeism, 2. Presenteeism, 3. Work productivity loss, and 4. Activity impairment.

WPAI :GH outcomes are expressed as impairment percentages, with higher numbers indicating greater impairment and less productivity (ie, worse outcomes). The scoring is as follows:

1. Absenteeism: Percent work time missed due to problem: $100 * [Q2 / (Q2 + Q4)]$.
2. Presenteeism: Percent impairment while working due to problem: $100 * [Q5 / 10]$.
1. Work productivity loss: Percent overall work impairment due to problem:
 $100 * \{Q2 / (Q2 + Q4) + (1 - Q2 / (Q2 + Q4)) * (Q5 / 10)\}.$
3. Activity impairment: Percent activity impairment due to problem: $100 * (Q6 / 10).$

Where,

Q2 = hours missed due to health problems,

Q4 = hours actually worked,

Q5 = degree health affected productivity while working,

Q6 = degree health affected regular activities.

Each score is interpreted separately.

AE-QoL

The AE-QoL consists of 17 items and subjects are asked to judge how often they have been restricted in different areas of their daily life because of angioedema and to give more details about their difficulties during the last 4 weeks. The rating for each of the 17 items consists of “Never”, “Rarely”, “Occasionally”, “Often” and “Very Often”. Responses are scored on a scale from 1 to 5, where 1 is “Never” and 5 is “Very Often”.

The items are assigned to four dimensions - Functioning, Fatigue/Mood, Fears/Shame and Nutrition - as follows:

Dimensions	Item
Functioning	1. Impairment of work
	2. Impairment of physical activity
	3. Impairment of spare time activities
	4. Impairment of social relations
Fatigue/Mood	6. Difficulties of falling asleep
	7. Waking up during the night
	8. Feeling tired during the day
	9. Difficulties in concentrating
	10. Feeling downhearted
Fears/Shame	12. Feeling burdened at having swellings
	13. Fear of new suddenly appearing swellings
	14. Fear of increased frequency of swellings
	15. Ashamed to visit public places
	16. Embarrassed by the appearance of swellings

	17. Fear of long term negative drug effects
Nutrition	5. General limitations in foods and eating
	11. Limitations in the selection of food and beverages

It is possible to calculate four individual AE-QoL scores for the four different dimensions or to calculate one AE-QoL total score (Item 1 to Item 17).

The four AE-QoL scores for the four different dimensions as well as the AE-QoL total score are calculated by using the following formula:

$$[(\Sigma \text{ items} - \min \Sigma \text{ items}) / (\max \Sigma \text{ items} - \min \Sigma \text{ items})] \times 100$$

where

$\Sigma \text{ items}$ is the sum of all non-missing item scores within a dimension or all items, respectively,

$\min \Sigma \text{ items}$ is the sum of the minimum score 1 which is added up as many times as there are non-missing item scores within a dimension or all items, respectively,

$\max \Sigma \text{ items}$ is the sum of the maximum score 5 which is added up as many times as there are non-missing item scores within a dimension or all items, respectively.

For the following example for the dimension “Functioning”:

Item 1: Occasionally (3)

Item 2: Rarely (2)

Item 3: Often (4)

Item 4: Very Often (5)

the AE-QoL score would be calculated by

$$\Sigma \text{ items: } (3+2+4+5) = 14$$

$$\text{min } \Sigma \text{ items: } (1+1+1+1) = 4$$

$$\text{max } \Sigma \text{ items: } (5+5+5+5) = 20$$

resulting in $[(14 - 4) / (20 - 4)] \times 100 = 62.5\%$.

The four AE-QoL scores for the four different dimensions should not be calculated if more than one item is missing in that dimension. The AE-QoL total score should not be calculated if more than 4 items are missing.

The scores are range between 0 and 100 %. The higher the percentage the stronger the impairment the subject has.

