2.0	02 Oct 2025	[name]	
• Updates due to Protocol Amendment 1 to consider transition to autoinjector device and dose modifications no longer being permitted.• Inclusion of additional subgroups and analysis windows.• Correction of the description of the Treatment Satisfaction for Medication Questionnaire version II derivations.• Consolidation of all information regarding adverse events in Section 11.• Formatting and abbreviation edits.• New analysis for number and proportion of attack-free days.• Removal of most Corona Virus Disease 2019 related analysis.• Removal of Mixed Model and Sidak correction of confidence intervals for analysis of quality of life endpoints.

2 List of Abbreviations

Abbreviation	Definition
ADaM	Analysis Data Model
AE	Adverse Event
AE-QoL	Angioedema Quality of Life Questionnaire
AESI	AE of Special Interest
AI	Autoinjector
ATC	Anatomical Therapeutic Chemical
ATS	All Treated Subjects
AUC	Area under the Curve
AUC _{0-30days}	Area under the Concentration-time curve from 0-30 days
BMI	Body Mass Index
CDISC	Clinical Data Interchange Standards Consortium
CI	Confidence Interval
C _{max}	Maximum Concentration
COVID-19	Corona Virus Disease 2019
CSR	Clinical Study Report
DBL	Database Lock
eCOA	electronic Clinical Outcome Assessment
eCRF	Electronic Case Report Form
EOS	End of Study
EOT	End of Treatment
FXII(a)	(Activated) Factor XII
HAE	Hereditary Angioedema
ICH	International Conference on Harmonisation
ID	Identifier
IDMC	Independent Data Monitoring Committee
IGART	Investigator's Global Assessment of Response to Therapy
ISR	Injection site reaction
IRT	Interactive Response Technology
MCID	Minimal Clinically Important Difference
MedDRA	Medical Dictionary for Regulatory Activities
nC1-INH	Normal C1-esterase inhibitor
NSD	Needle safety device
PARM	Planned Analysis Review Meeting
PD	Pharmacodynamics

Abbreviation	Definition
PK	Pharmacokinetics
PP	Per Protocol
PT	Preferred Term
QoL	Quality of Life
SAE	Serious Adverse Events
SAP	Statistical Analysis Plan
SC	Subcutaneously
SD	Standard deviation
SDTM	Study Data Tabulation Model
SGART	Subject's Global Assessment of Response to Therapy
SMQ	Standardised MedDRA Query
SOC	System Organ Class
TEAE	Treatment Emergent Adverse Event
TFL	Tables, figures, listings
Tmax	Time to Maximum Concentration
TSQM II	Treatment Satisfaction for Medication Questionnaire version II
WHODrug Global	World Health Organization Drug Global

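### The TSQM II EFFECT formulas in SAP 10.3.2 subtract constants that cannot give the stated 0 to 100 range

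*SAP*

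**What the plan says.** SAP 10.3.2 describes the TSQM II as 11 items: eight on three specific scales, two on a global scale, and Item 3, a yes/no question on side effects that enters no formula. It sets one target range for every scale: "Scale scores are calculated for each scale and are transformed into scores ranging from 0 to 100".

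It then gives two formulas per scale, one for complete answers and one for a single missing item. With typesetting marks left in, EFFECT with both items is "Item 1} + \text{Item 2}) - 3] \text{ divided by } 12 \times 100", and with one item missing "Sum of Available Items}) - 2] \text{ divided by } 6 \times 100". GLOBAL with both items is "Sum of Item 10 to Item 11}) - 2] \text{ divided by } 12 \times 100", and with one missing "Sum of Available Items}) - 1] \text{ divided by } 6 \times 100".

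SAP 10.3.2.1 presents the scores by visit and as change from baseline, separately for treatment-naïve and non-treatment-naïve subjects. It also reports the proportion reaching a minimal clinically important difference (MCID), which for the TSQM is half the baseline SD. The SAP does not print the response coding of any TSQM item.

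The modification history in SAP Section 1 lists, for version 2.0, "Correction of the description of the Treatment Satisfaction for Medication Questionnaire version II derivations".

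**The concern.** EFFECT and GLOBAL have the same number of items and the same divisors but subtract different constants. EFFECT carries the constants of the three-item scales (3, or 2 with one missing) on two-item divisors. At most one of the two patterns can give the stated range, and GLOBAL's is the one that fits the remaining scales.

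At stake are the EFFECT levels reported at each visit, which would be too low and could be negative on a scale declared to start at zero. The shift also differs between complete and one-item responses, so a change between visits can be partly an artefact of how many items were answered. The error stands in a part of the SAP that version 2.0 records as corrected, so it may not be looked at again.

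**Working it through.** **Inputs, all from SAP 10.3.2.** For each scale: number of items, constant subtracted and divisor, complete and with one item missing. EFFECT is confirmed as a two-item scale by the item count: Items 1-2, 4-6 and 7-9 give 2 + 3 + 3 = 8, plus two GLOBAL items and Item 3 makes 11.

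**Step 1. What coding does each formula imply?** A score (sum - c)/d x 100 over k items runs from 0 to 100 only if the average item minimum is c/k and the average item span is d/k.

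| Scale | Answered items k | c | d | Minimum c/k | Span d/k |
|---|---|---|---|---|---|
| SIDE EFFECTS, complete | 3 | 3 | 12 | 1 | 4 |
| SIDE EFFECTS, one missing | 2 | 2 | 8 | 1 | 4 |
| CONVENIENCE, complete | 3 | 3 | 18 | 1 | 6 |
| CONVENIENCE, one missing | 2 | 2 | 12 | 1 | 6 |
| GLOBAL, complete | 2 | 2 | 12 | 1 | 6 |
| GLOBAL, one missing | 1 | 1 | 6 | 1 | 6 |
| EFFECT, complete | 2 | 3 | 12 | **1.5** | 6 |
| EFFECT, one missing | 1 | 2 | 6 | **2** | 6 |

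The stated range is reproduced for three scales, each with a minimum of 1 in both formulas. EFFECT needs 1.5 in one and 2 in the other.

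**Step 2. Can any coding rescue EFFECT?** Let the two items have minima a and b. The complete formula needs a + b = 3. The one-missing formula, which must work whichever item is left, needs a = 2 and b = 2, so a + b = 4. Both cannot hold. This does not depend on what the coding is.

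**Step 3. Ranges under 1-7 coding.** The span of 6 comes from EFFECT's own divisors and the minimum of 1 from the other three scales.

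- Both items: (2 - 3)/12 x 100 = -8.33, to (14 - 3)/12 x 100 = 91.67.
- One missing: (1 - 2)/6 x 100 = -16.67, to (7 - 2)/6 x 100 = 83.33.

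Other codings, as a range:

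| Coding | Both items | One missing |
|---|---|---|
| 0-6 | -25 to 75 | -33.33 to 66.67 |
| 1-5 | -8.33 to 58.33 | -16.67 to 50 |
| 1.5-7.5 | 0 to 100 | -8.33 to 91.67 |
| 2-8 | 8.33 to 108.33 | 0 to 100 |

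**Step 4. Effect on change.** Against constants 2 and 1, the printed formulas are low by 1/12 x 100 = 8.33 points (both items) and 1/6 x 100 = 16.67 points (one missing).

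- Both items at both visits: -8.33 - (-8.33) = 0. The change is correct.
- One item at both visits: -16.67 - (-16.67) = 0. No artefact from the constant.
- Two items at one visit, one at the other: 16.67 - 8.33 = 8.33 points of spurious change, downward if the one-item visit is later and upward if it is earlier.

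For example, a subject who chooses 4 throughout scores (8 - 3)/12 x 100 = 41.67 with both items and (4 - 2)/6 x 100 = 33.33 with one. With constants 2 and 1 both scores are 50.

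**Step 5. Effect on the MCID.** A shift of 8.33 points common to all subjects leaves the baseline SD, and so half of it, unchanged. For a subject with a differing number of answered items, 8.33 points alone would equal the threshold at a baseline SD of 2 x 8.33 = 16.67. The documents give no baseline SD, so this is illustrative only.

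**The case against.** The strongest reply is that the harm is small. With complete answers the error is one constant. It cancels in change from baseline, in the confidence intervals for differences and in the half-SD MCID. The TSQM II is completed on an electronic device at the site (Protocol 8.2.1.5 and 8.2.2), and the documents do not say whether an item can be skipped, so mixed one-item and two-item subjects may be few or absent. All of this stands. It means that a reader who infers that EFFECT change scores are biased in general goes beyond the documents. What remains is the level of EFFECT at every visit, and change in mixed responders, whose number is unknown.

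A second reply is that the figures rest on an unprinted coding. That is right for the exact endpoints, but not for the contradiction, which Step 2 shows under any coding. A misread digit is also unlikely, because both EFFECT constants are off by one in the same direction.

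Two further readings are tempting and not supported:

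- **SIDE EFFECTS.** A reader might infer that subjects who answer no to Item 3 leave Items 4 to 6 blank and are then unscored, so that the scale describes only people with side effects. The SAP states no such skip. Nor does it give the direction of the TSQM scales, so a rule assigning such subjects a fixed score has no source here.
- **Interim results.** A reader might infer that interim TSQM output is wrong. Neither the version 1.0 formula nor the program code is visible, so nothing shows that this formula was used.

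**Conclusion.** The EFFECT derivation is wrong as written: it contradicts the range stated just before it, and its two formulas contradict each other. Under 1-7 coding, by-visit EFFECT levels are 8.3 points too low with both items answered and 16.7 points too low with one. The only error in change is 8.3 points, in subjects whose number of answered items differs between the two visits.

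The existence of the error needs no assumption about coding. Its size rests on 1-7 coding, inferred from EFFECT's own divisors and from the other scales.

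A reader might take an arithmetic error in a prespecified score as a threat to the study's conclusions. The documents do not support that. The TSQM II is exploratory (Protocol 2.3.2; SAP 4.1), no confirmatory test is planned (SAP 10.4), and the primary safety endpoint and all secondary endpoints, including SGART, do not use it. This is a should-fix point.

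**What to change.** In SAP 10.3.2, replace the EFFECT formulas with:

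- both items answered: [(Item 1 + Item 2) - 2] / 12 x 100;
- one item missing: [(available item) - 1] / 6 x 100.

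These match GLOBAL. Under 1-7 coding they give (2 - 2)/12 = 0 to (14 - 2)/12 = 100%, and (1 - 1)/6 = 0 to (7 - 1)/6 = 100%. Print the response coding of the TSQM II items, so that all scale ranges can be checked from the text.

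Then compare the program code, and any TSQM output already produced, with the corrected formulas. Output needs to be redone only if it used the constants 3 and 2.

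The cost is two constants and one sentence in the SAP, plus a short code check. No data collection or other analysis changes.

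### The TSQM II EFFECT scale is scored with the offsets of a three-item scale, so it cannot run from 0 to 100 as the SAP says

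*SAP*

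**What the plan says.** SAP section 10.3.2 describes the instrument as follows: "The TSQM II consists of 11 items of which 8 items are made up of 3 specific scales". Two further items form the global satisfaction scale, and Item 3 is a yes/no question on side effects. All scales share one target range: "Scale scores are calculated for each scale and are transformed into scores ranging from 0 to 100".

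The section then gives a scoring formula for each scale, with a second version for one missing item:

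- EFFECT (Items 1 and 2): sum minus 3, divided by 12; with one item missing, minus 2, divided by 6.
- SIDE EFFECTS (Items 4 to 6): sum minus 3, divided by 12; with one missing, minus 2, divided by 8.
- CONVENIENCE (Items 7 to 9): sum minus 3, divided by 18; with one missing, minus 2, divided by 12.
- GLOBAL (Items 10 and 11): sum minus 2, divided by 12; with one missing, minus 1, divided by 6.

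Each result is multiplied by 100. The missing-item rule reads: "If more than one item is missing from any subscale then the subscale will not be calculated". A two-item scale is therefore still scored from a single answer.

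Section 10.3.2.1 summarises the scores by visit, the changes from baseline with 95% confidence intervals, and the proportion of subjects reaching a minimal clinically important difference (MCID). For the TSQM, that difference is half the baseline standard deviation.

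**The concern.** To map a sum of items to 0 to 100, the formula must subtract the smallest possible sum and divide by the width of the possible range. SIDE EFFECTS, CONVENIENCE and GLOBAL subtract 1 per answered item. EFFECT subtracts one more than that, both on complete forms and with an item missing. It combines the divisors of a two-item scale with the offsets of a three-item scale.

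Programmed as written, the by-visit EFFECT levels would be wrong for every subject who completes the questionnaire. The least favourable answers would give a negative score, and the most favourable could not reach 100. The error also differs between complete and incomplete forms, so part of it can pass into change from baseline and the MCID proportion.

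The SAP's modification history lists a correction of the TSQM II derivations in version 2.0, so a programmer may assume that these lines have already been checked.

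**Working it through.** **Number of EFFECT items.** The three specific scales hold 8 items. SIDE EFFECTS takes Items 4 to 6 and CONVENIENCE takes Items 7 to 9, which leaves 8 - 3 - 3 = 2. The EFFECT formula itself names only Items 1 and 2.

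**Item coding.** The SAP does not state it, so it is inferred. The EFFECT divisors give a width of 12/2 = 6 per item on complete forms and 6/1 = 6 with one missing. GLOBAL has the same widths, and its offsets give an item minimum of 2/2 = 1 and 1/1 = 1. The implied coding is 1 to 7. The same reasoning gives 1 to 7 for CONVENIENCE (18/3 = 6) and 1 to 5 for SIDE EFFECTS (12/3 = 4).

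**Ranges as written**, from 100 × (sum - offset) / divisor at the smallest and largest sum:

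| Scale | Complete form | One item missing |
|---|---|---|
| SIDE EFFECTS | (3-3)/12 = 0 to (15-3)/12 = 100 | (2-2)/8 = 0 to (10-2)/8 = 100 |
| CONVENIENCE | (3-3)/18 = 0 to (21-3)/18 = 100 | (2-2)/12 = 0 to (14-2)/12 = 100 |
| GLOBAL | (2-2)/12 = 0 to (14-2)/12 = 100 | (1-1)/6 = 0 to (7-1)/6 = 100 |
| EFFECT | (2-3)/12 = **-8.33** to (14-3)/12 = **91.67** | (1-2)/6 = **-16.67** to (7-2)/6 = **83.33** |

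(Results are after multiplication by 100.) The stated range is reproduced for three scales and fails for EFFECT.

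**Could another coding rescue EFFECT?** At a width of 6 per item, the complete formula starts at 0 only if the item minimum is 3/2 = 1.5. The one-missing formula starts at 0 only if it is 2/1 = 2. Both cannot hold.

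| Item minimum | Complete form | One item missing |
|---|---|---|
| 0 | -25 to 75 | -33.33 to 66.67 |
| 1 | -8.33 to 91.67 | -16.67 to 83.33 |
| 1.5 | 0 to 100 | -8.33 to 91.67 |
| 2 | 8.33 to 108.33 | 0 to 100 |

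At least one EFFECT line therefore contradicts the stated range whatever the coding.

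**Error in each score.** One unit too much is subtracted: 100 × 1/12 = 8.33 points on a complete form and 100 × 1/6 = 16.67 points with one item missing.

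**Error in change from baseline:**

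- Both visits complete: -8.33 - (-8.33) = 0.
- One item missing at both visits: -16.67 - (-16.67) = 0.
- Missing only after baseline: -16.67 - (-8.33) = -8.33.
- Missing only at baseline: -8.33 - (-16.67) = +8.33.

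As an example, take a subject who answers 5 to every question answered at both visits. The complete form scores (10-3)/12 × 100 = 58.33 and the form with one missing item scores (5-2)/6 × 100 = 50.00. The result is a change of -8.33 although no answer changed.

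**After correction.** With offsets 2 and 1, EFFECT runs from 0 to 100 in both cases. The example gives (10-2)/12 × 100 = 66.67 and (5-1)/6 × 100 = 66.67, a change of 0.

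**The case against.** The strongest reply concerns weight. TSQM II is an exploratory endpoint and is summarised descriptively. It enters neither the primary nor any secondary endpoint, nor any analysis-set definition. EFFECT is one of four scales, only adults complete the questionnaire, and the item answers are collected, so the score can be recalculated without loss of data. On complete forms the offset is constant: it cancels in the change from baseline and leaves the baseline standard deviation behind the MCID unaltered. The documents do not say how often a single item is missing, so the 8.33-point change error has no known frequency. The SAP plans no comparison of one TSQM scale with another.

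All of that stands, and it confines the damage mainly to the by-visit EFFECT levels. It does not defend the formula.

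Two further replies fail. The item coding is indeed inferred, but the two EFFECT lines disagree with each other under any coding. A misread PDF is also unlikely: both EFFECT offsets are too large by exactly one unit, while both EFFECT divisors and all six formulas for the other scales are coherent.

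**Conclusion.** The EFFECT formula is wrong as written. If it is programmed literally, each EFFECT level is 8.33 points too low on a complete form and 16.67 points too low with one item missing. Changes from baseline are wrong by 8.33 points, in either direction, only when an item is missing at one of the two visits and not at the other. The MCID proportion is affected through those changes, and through the baseline standard deviation if some baseline forms have a missing item. With complete forms throughout, changes and MCID are correct.

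These sizes rest on the inferred coding of 1 to 7. The contradiction between the two EFFECT lines does not. The documents do not show whether SAP version 1.0 contained the same error or whether any interim output used this formula.

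**What to change.** In SAP section 10.3.2, replace the two EFFECT lines by:

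- both items present: [(Item 1 + Item 2) - 2] / 12 × 100;
- one item missing: [(available item) - 1] / 6 × 100.

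State the item coding for each scale next to its formula, after checking it against the instrument's response options. Add a check in the analysis dataset that every TSQM II scale score lies between 0 and 100. SAP section 4.5.1 has the interim outputs follow the final SAP, so check whether any of them used the present EFFECT formula and re-derive the scale where it did.

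The cost is two numbers in the SAP, one derivation in the analysis dataset and one range check. No new data are needed.
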